10.3 Visit schedule

There is a screening visit and 7 study visits planned over the 52 weeks treatment period. A safety follow up will be conducted via phone 7 days after the final visit.

10.3.1 Screening & Randomisation

After giving his/her Informed Consent, the patient may be selected based on inclusion and exclusion criteria for the study at visit 1. The shipment or transfer of HRCT for review can be

organised before the screening visit provided the participant has given and signed his Informed Consent. The screening is up to 6 weeks.

The participants will be randomised at visit 2 if all inclusion and exclusion criteria are fulfilled. The results of laboratory parameters from visit 2 may only become available 24 to 72 hours after visit 2. Therefore, laboratory results from visit 2 cannot qualify as exclusion criteria. However, in case these results would retrospectively fulfil an exclusion criterion, the patient will be withdrawn unless continuation is justified in writing by the Investigator.

10.3.2 Re-screening visit

If a subject fails to meet the screening criteria for reasons which the Principal Investigator judges to be anomalous or the result of a temporary factor, those test(s) may be repeated once at an ad hoc visit(s), providing the subjects is still within the six weeks screening window. Subjects who fail screening and are outside the six weeks screening window, whom the Principal Investigator judges to now meet the screening criteria will be permitted to undergo rescreening one additional time, with advanced approval from Syneos Health Medical Monitors.

If a re-screening visit occurs within 12 weeks of initial screening it is not required to repeat PFT and DLCO, if the PFT and DLCO measured at the initial screening have met study inclusion criteria.

10.3.3 Treatment period

There will be seven study visits during the treatment period as follows: at randomization/baseline (w0), w4, w8, w12, w26, w40, and w52. Details for the data collected at each visit are given in the time and events table (Section 2.2). Visits 3, 4 and 5 should occur within ± 3 days of the scheduled time point. Visits 6 and 7 should occur within ± 7 days of the scheduled time point.

10.3.3.1 Participants randomized prior to Protocol version 6.1_UK and eligible to continue participation

Participants who were already randomised and eligible to remain in GALACTIC-1 and continue to receive blinded study treatment (3 mg GB0139 or placebo) should attend visits as required by

Protocol version 5.1_UK until Protocol version 6.1_UK is approved. Once the amended ICF is approved they should be re-consented. Participants who have completed w52 visit by the time the Protocol version 6.1_UK is approved should attend a withdrawal visit as soon as possible followed by a phone call follow up as specified in the Protocol version 6.1_UK.

10.3.4 Study treatment completion and Follow-up period

Subjects will be considered to have completed the study treatment period if assessments according to the protocol at week 52 have been performed. At the end of the treatment period subjects will enter a follow-up period. Follow-up phone call can be performed from 7 days and up to 14 days after the last study visit or withdrawal visit.

Additional individual visits may be scheduled by the treating physician on a case by case basis. Data collected at these visits will be recorded as unscheduled visits in the eCRF.

At all scheduled visits, study site staff will collect treatment patterns and outcomes, vital status, clinical events, AE/SAE data from the charts of study subjects followed at the participating sites.

10.4 Study procedures

10.4.1 Data collection

An electronic case report form (eCRF) system will be utilized for data collection, monitoring, and quality control. Data validation will be programmed in the eCRF system to automate data queries. The physician or assigned study personnel will complete the eCRFs at every visit, and as required by the protocol.

If clarifications are needed, queries will be raised either by the monitor of the study or the assigned data management team, through the built-in query management functionality in the eCRF. The physician or assigned study personnel will be required to respond to these queries through the eCRF system.

Subject data collected on eCRFs during the study will be recorded in an anonymous fashion to ensure subject confidentiality. The physician must maintain source documents where relevant for

each subject in the study, consisting of all demographic and medical information, and keep the written informed consent form. All information on the eCRFs must be traceable to these source documents in the subject's medical file.

Initiation of the participating sites will be performed by the designated CROs. Before study initiation, a CRO representative will review the protocol, the CRF and the eCRF system with the physicians and their staff. CROs will follow streamlined SOPs that have been reviewed and approved by Galecto.

Concomitant or prior medications entered into the database will be coded using the World Health Organization (WHO) Drug Reference List. Medical history/current medical conditions and adverse events will be coded using the Medical Dictionary for Regulatory Activities (MedDRA) terminology.

10.4.2 Informed Consent

Each subject must provide written informed consent before any study-required procedures are conducted, and before the diagnostic HRCT can be sent for central review.

10.4.3 Subject Demographics

Subject demographics will be collected at screening visit 1.

- Age at baseline
- Gender
- Height and body weight (for BMI computation)

10.4.4 Medical History

During the Screening period, a complete medical history will be compiled for each subject. The following variables will be collected:

- Smoking history, recorded in pack-years
- Pre-existing conditions

- Time of IPF diagnosis by HRCT or surgical lung biopsy
- Time of start of treatment with pirfenidone or nintedanib (as appropriate)
- Time point and reason for discontinuation of treatment with pirfenidone or nintedanib (as appropriate)
- Any episode of acute exacerbation in the subject's IPF context during three months prior to randomization
- Any medication used prior to screening including vaccinations

10.4.5 Physical Examination

A physical examination will be completed as per standard of care at all visits.

10.4.6 Vital Signs

Vital sign measurements include supine (after at least 5 minutes in this position) measurements of diastolic and systolic blood pressure, heart rate, and body temperature. They will be conducted at all visits.

10.4.7 Health-related Quality of Life Questionnaires

Three patient-reported assessments related to symptoms and quality of life will be collected during the study. A version of each will be to the site and will be completed by each subject at the visits as per the T&E table Section [2.2](#)

- St George's Respiratory Questionnaire (SGRQ) a validated QoL for IPF
- The Short Form Health-36 survey
- The University of California San Diego, shortness of breath questionnaire (UCSD-SOBQ)

10.4.8 12-Lead Electrocardiogram

Safety monitoring by ECG will be performed using site local equipment. PR interval, QRS duration, QT interval and QTcF are required to be evaluated.

10.4.9 Clinical Laboratory Evaluations

Clinical laboratory evaluations will be performed by a central laboratory as outlined below. Blood samples for analysis of the clinical chemistry and hematological parameters, urinalysis and biomarkers are shown in [Table 2](#), [Table 3](#) and [Table 4](#).

Table 2: Clinical Chemistry and Hematology Tests

Hematology	Serum Chemistry	
Hematocrit	Albumin	Glucose
Hemoglobin	Alkaline phosphatase (ALP)	Potassium
Leukocytes with differential count	Aspartate transaminase (AST)	Sodium
Platelet (count)	Alanine transaminase (ALT)	
	Bilirubin (total)	
	Calcium	
	Creatinine	

Table 3: Clinical Urinalysis Tests

Urinalysis		
	Bilirubin	pH
	Glucose	Protein
	Ketones	Specific gravity
	Leukocytes	Turbidity and color
	Nitrite	Urobilinogen
	Occult blood	

Results are recorded qualitatively as: -, +, ++, +++

10.4.10 Pregnancy Test

A serum pregnancy (choriogonadotropin beta) test will be completed by all females of child-bearing potential during screening; this test must be negative for the subject to be enrolled. Urinary pregnancy tests will then be repeated at various times during the study as specified in the Time & Events table.

Any occurrence of a pregnancy in a subject undergoing treatment in the GALACTIC-1 study must be reported according to the rules agreed upon with the designated CRO within 24 hours of learning of its occurrence. The pregnancy should be followed-up via fax or email to determine outcome, including spontaneous or voluntary termination, details of the birth, and the presence or absence of any birth defects, congenital abnormalities, or maternal and/or new-born complications.

Pregnancy should be recorded on a *Pharmacovigilance Pregnancy Form* and reported by the treating physician or other involved health care professional to Galecto's Pharmacovigilance (PV) representative. In case of any congenital abnormality, birth defect or maternal and new-born complications, the possible relationship to the Galecto drug should be reported.

Additionally, any SAE experienced during pregnancy must be reported into the eCRF system.

Note: should the eCRF system become non-operational, the site must complete the appropriate paper *Serious Adverse Event Form*. The completed form is then faxed/mailed within 24 hours of the Investigator's or site's awareness; however, the reported information must be entered into the eCRF system once it becomes operational. Please see Section 11.2 for PV reporting information.

10.4.11 Biomarkers

A serum sample for the assessment of biomarkers will be collected at baseline (visit 2) and weeks 4, 12, 26 and 52. The list in Table 4 gives *examples* of biomarkers potentially related to Galectin-3 activity and/or IPF disease severity/prognosis. More detail on the rationale for including such biomarkers is described in [Appendix 2](#) (Section 18.0). Ultimately, individual biomarkers may be added to or removed from this list.

Table 4: Biomarker Panel

Serum Biomarkers	
Gal-3	KL-6
Collagen neoepitopes	PAI-1
YKL-40	PDGF-BB
MCP-1	CCL-18
CA-125	CA-19

10.4.12 Genetics Sample

All subjects will be asked for a blood sample for genetic assessment. However, this is not mandatory for the subject to participate in the study. A single sample will be taken at visit 2 or at any visit throughout the study and processed or stored after separate informed consent is given in accordance with local ethical and regulatory requirements. The sample will be anonymised, meaning there will be no way to trace back to the identity of the donor. Samples will be stored for up to 15 years after the end of the study or until there is no more material available for tests.

10.4.13 Spirometry

Equipment and manual will be provided by Clario (previously ERT). Data will be centrally evaluated by Clario.

10.4.14 Pulse Oximetry

Pulse oximetry will be measured using sites local equipment.

10.4.15 DLCO

Sites use local equipment to measure DLCO using a manual provided by Clario. Data will be centrally overread by Clario.

10.4.16 6MWT

Test manual will be provided by Clario.

10.4.17HRCT central overread

HRCT will be reviewed by an independent Chest radiologist, assigned by Clario, who will assess according to the ATS/ERS/Fleischner criteria [1-3].

10.4.18 Concomitant Medications and Procedures

Medications including vaccination used by the subject will be recorded in the electronic case report form (eCRF) to cover screening period and then prospectively at all study visits (treatment and follow up periods) until study completion/withdrawal. See Section 8.3.2 for a list of medications and therapies that are prohibited during the study.

10.4.19 Adverse Events

Monitoring of AEs, serious and nonserious, will be conducted throughout the study as specified in the Time and Events Table (Section 2.2). Refer to Section 11.0 for details regarding definitions, documentation, and reporting of pretreatment events (PTEs), AEs, and SAEs.

10.5 Discontinuation of study treatment

Temporary discontinuation of GB0139 for <2 weeks will be permitted, if for reasons other than those stated below. The reason for discontinuation should be documented in the eCRF.

Treatment with study drug may be permanently discontinued for any of the following reasons:

- Persistent non-adherence by subject
- Adverse event assigned to the investigational drug
- Overall unsatisfactory therapeutic response
- Study terminated by sponsor
- Withdrawal by subject
- Lost to follow-up
- Other (cause to be elaborated on in the subject's file)

In all cases, participants should be encouraged to discuss any potential study treatment discontinuation with the investigator prior to stopping treatment. If considered medically appropriate by the PI, participants who have been withdrawn from study treatment can remain in the study, resume their usual standard of care treatment for IPF, if applicable, and complete scheduled visits and study assessments up to the follow up phone call.

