6.2 Number of Participants

Approximately 141 participants in total will be randomized in GALACTIC-1.

Participants are considered evaluable if they have taken at least one dose of the double-blind treatment.

Participants who prematurely discontinue double-blind study treatment after randomization can remain in the study and complete the remaining scheduled visits, if possible.

Any participants who withdrawn from the study after randomization cannot be replaced and re-screened.

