10.6 Withdrawal of Subjects from the Study

Subjects may withdraw for the following reasons:

- Lost to follow-up
- Study terminated by sponsor
- Withdrawal by subject
- Completed study
- Death
- Lung transplant
- Other (cause to be elaborated on in the subject's file)

All study procedures outlined for the withdrawal visit will be completed as specified in the Time and Events Table (Section 2.2). The primary reason for study drug discontinuation will be recorded on the eCRF.

Following the study withdrawal, no new information will be collected from the withdrawn subject and added to the existing data or any database.

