14.4.1 Analysis of Primary Efficacy Endpoint

The primary endpoint is described in Section 9.1. The primary efficacy analysis is a random coefficient regression (random slopes and intercepts) model. Treatment and baseline FVC (mL) will be included as a covariate in the analysis model. Other covariates such as age, and gender will be included as covariates unless their inclusion violates model assumptions or impacts stability. Baseline FVC is defined as the FVC result recorded at Visit w0/baseline, unless missing in which case the latest FVC before randomization in the subject's chart result will be used.

The decrease in FVC is assumed to be linear within each subject over 52 weeks. The intercepts and slopes will be assumed to be normally distributed with arbitrary covariance matrix. The within-subject error will be assumed to be independent and normally distributed with mean zero and a common variance. The Kenward-Roger approximation will be used to estimate denominators degrees of freedom.

Section 14.8 details of the approaches to handling of missing data are given.

Significance tests will be based on least-squares means; p-values and two-sided 90% confidence intervals for the difference between the treatment groups will be presented. An intent-to-treat principle will be used. Analyses will be implemented using SAS® Version 9.4 or higher. The assumptions for the primary analysis of decline in FVC will be tested; details will be provided in the SAP. The primary analysis will be based on observed data (but including retrieved drop out

measurements) and will assume remaining missing data are missing at random. The effect of missing data will be investigated using multiple imputation methods which assume that subjects who discontinue treatment will no longer benefit from it in the future. See Section 14.8 for further details of these sensitivity analyses.

Subgroup analyses will be fully specified in the SAP and will include:

- Age
- Gender
- Race
- Ethnicity
- Previous treatment with pirfenidone and/or nintedanib
- Recruitment cohort (e.g., pre- or post- DSMB cutoff, and pre- or post-Protocol version 6.1_UK)

A cumulative distribution plot will be provided, showing the percentage of subjects by change from baseline in FVC in mL at week 52.

Data will be summarized graphically and using summary statistics.

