14.8 Handling of Missing Data

This section describes the estimands approach for the primary analysis and associated sensitivity analyses using the Detailed Clinical Objectives framework described by Bell [51].

The trial will compare GB0139 3 mg with Placebo in patients with IPF not currently treated with pirfenidone or nintedanib. The primary objective is to demonstrate superiority of GB0139 3 mg for the mean annual rate of decline in FVC in mL. A composite strategy will be taken to patient deaths with FVC attributed the lowest value recorded in the trial when a patient dies.

Three specific inter-current events (ICEs) are anticipated during the trial: death, treatment discontinuation, and initiation of pirfenidone or nintedanib. The handling of these ICEs for the treatment effect of primary interest and planned sensitivity analyses for the primary endpoint are described in [Table 5](#).

Table 5: Handling of anticipated ICEs for treatment effect of primary endpoint

Treatment effect	Description	Death	Treatment discontinuation	Initiation of IPF therapy
Primary (ICEs of treatment discontinuation or additional IPF therapy)	Randomized and treated patients with treatment policy applied for intercurrent events other than death	FVC attributed the lowest value recorded in the trial when a patient dies	Analysis will include all available FVC measurements after randomised treatment discontinuation	Analysis will include all available FVC measurements after initiation of additional IPF therapy
Sensitivity 1 (on-treatment)	Randomized and treated patients while on randomised treatment	FVC attributed the lowest value recorded in the trial when a patient dies	Analysis will exclude any FVC measurements after randomised treatment discontinuation	Analysis will exclude any FVC measurements after initiation of additional IPF therapy
Sensitivity 2 (ICE of Death)	Randomized and treated patients while on	FVC attributed value of 0	Analysis will exclude any FVC measurements after	Analysis will exclude any FVC measurements after

	randomised treatment	when a patient dies	randomised treatment discontinuation	initiation of additional IPF therapy

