### 7.2.2 Main Estimand and Analysis

The primary analysis will test for superiority of GB0139 3mg compared to Placebo (Plc) for the annual rate of decline in FVC in mL over 52 weeks in subjects not receiving pirfenidone or nintedanib at baseline in the mITT Set. The main estimand for the primary efficacy endpoint is as follows:

- Population: Primary Population, mITT set.
- Variable of interest: Change from baseline in FVC in mL over 52 weeks
- Intercurrent events:
  - Death: FVC attributed the lowest value recorded in the trial when a patient dies

	Plus-Project Statistical Analysis Plan	
	Protocol Number: GALACTIC-1	Version: 1

- Treatment Discontinuation: Analysis will include any FVC measurements after randomised treatment discontinuation
- Initiation of additional IPF therapy (nintedanib or pirfenidone): Analysis will include any FVC measurements after initiation of additional IPF therapy
- Summary measure: Comparison of slopes assessed through the treatment by time interaction.

The null hypothesis is:

$H_0$ : There is no difference in the annual rate of decline in FVC in mL between GB0139 3mg and Plc

The alternative hypothesis is:

$H_a$  : There is a difference in the annual rate of decline in FVC in mL between GB0139 3mg and Plc

A restricted maximum likelihood (REML) approach will be used, with a random coefficient regression (random slopes and intercepts) model fitted to test the hypotheses. The decrease in FVC is assumed to be linear within each subject over 52 weeks [5].

Baseline FVC and time will be fitted as continuous covariates. The treatment group and the interaction term for time by treatment group will be added as fixed effects. Random subject intercept and time effects will be fitted and will be assumed to be normally distributed with arbitrary covariance matrix. The within-subject errors will be assumed to be independent and normally distributed with mean zero and a common variance. The Kenward-Roger approximation will be used to estimate denominators degrees of freedom.

The statistical model will be as follows:

$$Y_{itk} = (\alpha + a_i + \tau_k) + \beta_f FVCb_i + (\gamma + \beta_3 T_3 + g_i) t + \varepsilon_{it}$$

where:

$Y_{itk}$  is the change from baseline measured for ith patient at time t (actual time) in treatment group k

$t$  is the time since randomization in years

$T_3 = 1$  if the subject is in the GB0139 3mg group, otherwise  $T_3 = 0$

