### 11.3 Primary Estimand Sensitivity and Tipping Point Analyses

A sensitivity analysis to test the robustness of the MAR assumption used in the main estimand analysis will be performed to assess the results with missing Week 52 FVC data.

Non-monotone missing data or missing data at other visits before week 52 will not be imputed. Multiple imputation will be used to handle missing data at week 52. The imputation model will be similar to the statistical model of the primary analysis.

For the imputation of week 52 data that is not available for reasons other than the occurrence of an ICE, the imputation model will be run on the subset of patients who prematurely discontinued trial drug but have been followed up for FVC measurements at week 52. FVC measurements that remain unobserved due to ICEs will still be handled as described in Section 7.2.1. Table 5 below contrasts the MAR approach used in the main estimand analysis with the MNAR approach used in the sensitivity analysis.

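### Follow-up after stopping study drug is left to investigator discretion (Protocol 10.5) or feasibility (6.2), so the off-drug FVC that the primary estimand needs may be selectively observed

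*Protocol*

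**What the plan says.** On staying in the study after stopping drug:

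- Protocol 10.5: "If considered medically appropriate by the PI, participants who have been withdrawn from study treatment can remain in the study". No criteria are given. The same sentence also covers a return to usual IPF care.
- Protocol 6.2: "Participants who prematurely discontinue double-blind study treatment after randomization can remain in the study and complete the remaining scheduled visits, if possible". There is no investigator condition here, but also no requirement.
- Protocol 10.6: "Following the study withdrawal, no new information will be collected from the withdrawn subject and added to the existing data or any database".
- The Time and Events Schedule (Protocol 2.2) includes spirometry at the withdrawal visit.

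On the use of off-drug FVC:

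- Protocol 14.8, Table 5, primary treatment effect: "Analysis will include all available FVC measurements after randomised treatment discontinuation". FVC after the start of additional IPF therapy is handled in the same way. SAP 7.2.2 agrees: "Analysis will include any FVC measurements after randomised treatment discontinuation".
- Protocol 14.4.1 and SAP 7.2.2 treat whatever remains unobserved as missing at random (MAR).
- Protocol 8.3.1 allows nintedanib or pirfenidone after randomisation only once the inhaled study treatment has been withdrawn.

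On checking the MAR assumption, SAP 7.2.2.4 plans a multiple imputation if the amount of missing data causes concern. SAP 11.3 names its reference group as "the subset of patients who prematurely discontinued trial drug but have been followed up for FVC measurements at week 52".

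**The concern.** A treatment-policy estimand asks what happens to everyone randomised and treated, on drug or off it. It can be estimated without strong assumptions only if FVC continues to be collected after drug is stopped. Here collection depends on an opinion for which the protocol gives no criteria. Different investigators may apply it differently, and the participant's condition is a natural thing for them to weigh. A participant who is not kept in the study contributes an exit FVC at most, and nothing later.

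More than plain discontinuation is involved. For participants who follow Protocol 8.3.1, FVC after starting an antifibrotic also comes after study drug has stopped, so it falls under the same condition. Unsatisfactory therapeutic response is one of the listed reasons for stopping (10.5), so some of those affected may be people who were doing poorly. The death component of the estimand needs vital status, and collection of that also ends at study withdrawal.

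If those not kept go on to decline faster than the model predicts from their observed values, each arm's decline is understated. The 3 mg versus placebo difference is distorted if this happens to a different extent in the two arms.

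The point concerns participants who stop drug and are willing to stay. Code breaks, withdrawals after baseline laboratory results and withdrawal of consent are separate matters.

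**Working it through.** **The plan's own figure.** Inputs from Protocol 14.6 and SAP 3.1: 141 participants, 1:2 allocation, difference 100 mL, SD 240 mL, two-sided 10% level. If all 141 are split 1:2, that is 47 on placebo and 94 on 3 mg.

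- SE of the difference = 240 × √(1/47 + 1/94) = 42.9 mL.
- Power = Φ(100/42.9 − 1.645) = Φ(0.687) = 75.4%. With the noncentral t on 139 df it is 75.1%.

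The stated 75% is reproduced and is not in dispute. The SE serves below as a yardstick.

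**The two retention rules.** 10.5 is permissive and conditional on the investigator. 6.2 is permissive and conditional on feasibility. A site could follow either. Under both, a consenting participant off drug may leave follow-up without breach of the protocol.

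**Size.** The documents give no stopping rate, no share kept in follow-up and no off-drug slope, so every input here is an assumption. Let s be the share stopping drug, r the share of those kept, and g the extra decline in those not kept. If those not kept are in effect given the course of those kept, then

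understatement in an arm = s × (1 − r) × g.

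- One arm, s = 20%, r = 50%, g = 150-300 mL/yr: 0.20 × 0.5 × g = 15-30 mL/yr.
- Difference, s = 25% v 15%, r = 50% in both arms: (0.125 − 0.075) × g = 7.5-15 mL/yr, or 0.17-0.35 of the SE. The shift favours the arm that loses more participants.
- Equal s and r in both arms: the shift is 0.
- If only 10-20% of the loss comes from the 10.5 condition and the rest from consent withdrawal or loss to follow-up: 0.1 × 7.5 to 0.2 × 15 = 0.75-3 mL/yr.
- Harsher case, s = 30% v 15%, r = 50% v 90%, g = 300: (0.15 − 0.015) × 300 = 40.5 mL/yr. This needs retention to differ sharply between blinded arms. With r reversed (90% v 50%) the shift is (0.03 − 0.075) × 300 = −13.5 mL/yr, so the sign is not fixed either.

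All of these are upper-end values. They apply g to a full year although participants stop part-way, and they ignore what the random-slope model recovers from FVC already observed.

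**The imputation check.** The SAP describes it in ways that do not agree:

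- SAP 11.3 text: the subset model is for Week 52 values missing for reasons other than an intercurrent event (ICE). Values missing because of an ICE are referred to SAP 7.2.1, where treatment discontinuation is a named ICE.
- SAP Table 5: missing values take slopes from subjects who had an ICE and still have FVC.
- SAP 11.4, Step 1: slopes come from the primary model fitted to the observed data. Step 2 uses those slopes but points back to 11.3.

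If the named reference group is used, it has passed the same retention rule. It would also be small. With 10-30% stopping and 50-90% of them kept, it is 47 × 0.05 to 47 × 0.27 = 2.4-12.7 on placebo and 94 × 0.05 to 94 × 0.27 = 4.7-25.4 on 3 mg. The tipping-point step in SAP 11.3 moves values only from the MAR imputation towards this one, so it does not explore a course worse than both.

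**The case against.** The strongest reply is that nothing in the documents shows the condition removing anyone. 6.2 allows continued visits without it, and investigator opinion is not a listed reason for study withdrawal in 10.6 except through the open category. If investigators did act on observed FVC decline, the missingness would be close to MAR, which the random-slope model handles. An exit spirometry is scheduled, and known deaths receive an unfavourable FVC value. Arms are blinded, so selection may well be similar in both and cancel in the difference. The illustrative 7.5-15 mL/yr charges all loss to the condition, although consent withdrawal and loss to follow-up would occur under any wording.

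Most of this stands, and it limits both size and certainty. Two things remain. The primary model conditions only on treatment, time, baseline FVC and the FVC observed so far, whereas an opinion about medical fitness can draw on symptoms, admissions or other information outside the model. And the exit FVC does not supply the later off-drug course.

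Three stronger inferences are tempting, and the documents support none of them:

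- That the condition mainly removes the sickest participants. The text permits selection but says nothing about how the condition is applied, and the remaining visits include DLCO and a 6-minute walk as well as spirometry.
- That the imputation fills in lost participants from exactly those kept, and so cannot reveal the problem. The ICE wording and Step 1 of SAP 11.4 do not fit that reading, and under SAP 7.2.2.4 the analysis is conditional.
- That the investigator clause should simply be deleted. The same sentence governs a return to usual IPF care, so deletion would alter a clinical provision.

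**Conclusion.** The point holds as a gap in data collection. Sections 6.2 and 10.5 differ, neither requires follow-up of consenting participants off drug, and the primary estimand relies on the FVC that such follow-up would supply. Selection by patient condition and by site is possible; it is not shown. Bias in an arm's slope requires selection on later decline beyond what observed FVC predicts. Bias in the treatment difference also requires that selection to differ by arm.

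The size cannot be derived from the documents. With 25% v 15% stopping, half of them lost, all of that loss due to the rule, and a 150-300 mL/yr slope gap, the shift in the difference is at most about 7.5-15 mL/yr, against a 100 mL target and an SE of about 43 mL. It is smaller if the rule explains only part of the loss, and zero if the arms are affected equally. A reader might infer that the primary comparison is invalid, or biased in favour of GB0139; neither follows. The planned imputation may not reveal the problem, and its description needs reconciling in any case. The change is worth making because it is cheap and removes an avoidable source of missing data.

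**What to change.** - **Protocol 10.5 and 6.2.** Reconcile them by splitting the 10.5 sentence. Leave the wording on treatment and usual IPF care unchanged. State separately, in both sections, that every participant who stops study drug and still consents continues the scheduled visits to Week 52, with spirometry and vital status as the minimum. Allow a single procedure to be omitted on safety grounds, with the reason recorded.
- **Reporting.** Show, by arm, how many participants were off drug but on study, and how many of them have Week 52 FVC. SAP 6.1 already summarises treatment completion and study completion separately, so this adds one cross-tabulation.
- **SAP 11.3 and 11.4.** Make the ICE wording, SAP Table 5 and Step 1 agree on who is imputed and from which slopes.

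The cost is protocol and SAP wording, a reminder to sites, and visits for the additional off-drug participants. Those visits are already in the schedule, so no new procedure is added.
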